# 4.1.3.2 Multiple Testing

# (ICH E3; 9.7.1, 11.4.2.5. ICH E9; 2.2.5, FDA-2017)

The main analysis is defined as the analysis of covariance following general Model 1 [section 4.1.3.1] conducted on the main selection (FAS), on the primary endpoint (UNS) considered as a global endpoint aggregating both EDS and cataplexy symptoms. Secondary endpoints will be PDSS and the UNS-CTP subscale measuring the IMP effect on EDS and cataplexy, respectively. Two other secondary endpoints will be the weekly rate of cataplexy measured by the patient diary (WRC) and the MWT. All the other endpoints will be considered as exploratory and supportive.

The main endpoint (UNS) and the four secondary endpoints necessitate 5 tests. We will use the fixedsequence strategy testing the endpoints in the pre-defined order UNS, PDSS, UNS-CTP, WRC and MWT, each one tested at two-sided  $\alpha$ =.05 significance, moving to the following endpoint conditionally to a significant difference reached on the previous endpoints (FDA, section C.5). This strategy protects the results with type 1 risk bounded by P=.05.

Our choice is justified as follows: UNS constitutes a global appraisal of both EDS and cataplexy in pediatric narcolepsy and must regarded as a relevant general first endpoint. PDSS and UNS-CTP are validated scales to measure EDS alone and cataplexy alone, respectively. Conditionally to a significant effect on the main UNS endpoints, the effect of the IMP will be assessed on the two symptoms, separately. Finally MWT and WRC are alternative endpoints to measure EDS and cataplexy, respectively, and will be assessed conditionally to the significance obtained on UNS, PDSS and UNS-

CTP. Besides, EDS is a more frequent symptom, thus it was tested before cataplexy, and PDSS and UNS-CTP were shown with a higher power than MWT and WRC, respectively [ref-validation]

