# 4.1.6 Miscellaneous

- All the summarized tables mentioned in this SAP will be provided as RTF/HTML or WinWord compatible format (and not as text format). This allows direct insertion of these tables unchanged in the Clinical Study Report.

-Unless otherwise specified, the significance test will be conducted at a two-sided significance level of 0.05

-A third party statistician will independently review the Statistical Analysis Report before disclosing the results.

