# 4.2 Sample size calculation

(ICH E3; 9.7.2. ICH E9; 3.5)

The initial protocol was based in assuming a Pearson correlation coefficient of R=0.5 between prebaseline and final values of PDSS, two pre-baseline measurements [(V1+V2)/2] and two post-baseline measurements [(V6+V7)/2]. A standardized mean difference of at least 0.5 (considered as the minimum clinically significant difference) will be detected at a two-sided 0.05 confidence level with a power of at least 0.8, when the sample size/group is at least 20 and 40 patients for control and tested drug groups, respectively.

At a later stage, UNS measuring EDS and cataplexy was used as the primary outcome instead of the PDSS. As UNS was expected with a residual variability larger than PDSS, the initial power of .75 judged as too small, a recalculation of the sample size was performed on a standardized mean difference of 0.5 on the UNS (considered as the minimum clinically significant difference), a ratio 1:2, and a correlation R=0.4. Under these assumptions, and ANCOVA test at 0.05 two-sided confidence level, the probability of a significant effect will be found with a power of 0.85 when the sample size exceeds 36+72 patients for control and tested drug groups, respectively, thus a total of 108 patients.

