## Analysis:

MWT was right censored after 30 minutes, resulting into a truncated asymmetric distribution (Plazzi 2021).

A Cox proportional regression will be conducted in considering time to sleep onset (mean of the 4 tests at final visit) and survival response defined as non-response (0=patient remained awake until 30 minutes) and response (1=patient falling asleep before 30 minutes). Patients early terminating for treatment-related or -unrelated reason will be considered as responders or right-censored at the time of interruption, respectively. Center will be considered as a cluster variable in the Cox model to allow calculation of robust variance for the model assuming clusters with correlated observations [Andersen 1982, Therneau 2000].

This analysis will be done only in patients with at least a baseline value or a final value (V7 or the last on-study visit).

The same way as the primary analysis (Including sensitivity analyses) will be performed: MAR and MNAR imputation, center as fixed effect (in MAR imputation) and observed cases.

Descriptive statistics (mean values for each latency parameter and number of Sleep onset in SP) at baseline and V7 by treatment group will be provided.

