## Statistical elements:

For this comparison the following elements will be provided in a summary table:

- Estimate (standard error) of the difference between adjusted treatment group means.
- Two-sided 95% CI of the estimate.
- p-value (to be compared to 0.05).

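### The centre-clustered variance makes the confirmatory MWT test anti-conservative once it is reached, so the .05 bound is not assured at the last step of the fixed sequence

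*SAP*

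**What the plan says.** SAP 4.1.3.2 sets up a fixed sequence, "testing the endpoints in the pre-defined order UNS, PDSS, UNS-CTP, WRC and MWT", each at two-sided .05, "moving to the following endpoint conditionally to a significant difference reached on the previous endpoints". It then states: "This strategy protects the results with type 1 risk bounded by P=.05".

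SAP 4.5.3.2.4 analyses MWT by Cox regression on the mean sleep-onset time of the four tests, noting that "MWT was right censored after 30 minutes". On the variance it says: "Center will be considered as a cluster variable in the Cox model to allow calculation of robust variance for the model". The results list for this endpoint ends with "p-value (to be compared to 0.05". No small-sample correction, reference distribution or minimum number of centres is given. Centre as a fixed effect appears only as a sensitivity analysis. The same list asks for a difference in adjusted group means.

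For most endpoints, SAP 4.1.3.1 treats centre as a random intercept unless otherwise specified.

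**The concern.** A fixed sequence controls the familywise error only if each test has a true size of no more than .05. The sandwich variance clustered on centre is justified as the number of centres grows. With few centres, or centres of very unequal size, it is too small on average and too variable, and a comparison with 1.96 rejects too often.

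Treatment is allocated to individual patients, so clustering on centre is not needed to make the comparison valid. At stake are the p-value and confidence interval behind any confirmatory MWT claim, and the type 1 statement in SAP 4.1.3.2 as it applies to the fifth step.

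**Working it through.** **Inputs**
- Sample size: "36+72 patients for control and tested drug groups" (SAP 4.2), so 36 + 72 = 108.
- Level: "the significance test will be conducted at a two-sided significance level of 0.05" (SAP 4.1.6).
- Order and condition for moving on: SAP 4.1.3.2. Censoring at 30 minutes: SAP 4.5.3.2.4.
- Number of centres K: in neither document. Protocol 4.5.1 gives only a two-digit site number. Assumed range: 5 to 40.
- Allocation within centre: Protocol 4.5.2 does not mention blocking by centre. The main runs are unblocked.
- Reference distribution: not stated. An uncorrected Wald test, |z| > 1.96, is assumed.

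**Step 1. The plan's bound.** A false claim requires rejection of the first true null in the sequence. If every test has size at most .05, the familywise error is at most .05. The claim is therefore correct provided each test has its nominal size.

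**Step 2. A rough closed form.** The clustered variance is V = I⁻¹(Σ U_k U_k′)I⁻¹, with U_k the summed score residuals of centre k. Without correction it behaves roughly like a variance on K−1 degrees of freedom, shrunk by (K−1)/K. The approximate size is 2·P(T with K−1 df > 1.96·√((K−1)/K)):
- K = 5: 0.154
- K = 8: 0.109
- K = 10: 0.096
- K = 20: 0.071
- K = 30: 0.064

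This formula takes no account of unequal centre sizes.

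**Step 3. Simulation with no treatment effect.** The runs tabulated first use Weibull proportional-hazards data, censoring at 30 minutes, a baseline covariate, a centre effect of SD 0.3 on the log hazard, and 8,000 runs per setting. The Monte Carlo SE at 10% is √(0.1 × 0.9/8000) = 0.003. With unequal sizes some centres receive no patient; 20 nominal centres average 18.1 in use. The last column spans all the unblocked settings simulated at that K, including log-normal times and runs without the covariate.

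| K | Clustered, equal | Clustered, unequal | Model-based, equal / unequal | K/(K−1) and t(K−1), equal / unequal | Clustered, all settings |
|---|---|---|---|---|---|
| 5 | 0.171 | 0.207 | 0.058 / 0.052 | 0.059 / 0.081 | 17-22% |
| 8 | 0.123 | 0.151 | 0.059 / 0.054 | 0.058 / 0.078 | 12-15% |
| 12 | 0.103 | 0.121 | 0.059 / 0.060 | 0.063 / 0.077 | 9-12% |
| 20 | 0.082 | 0.093 | 0.054 / 0.052 | 0.058 / 0.067 | 8-10% |
| 30 | 0.073 | 0.084 | 0.056 / 0.054 | 0.058 / 0.062 | 7-9% |
| 40 | 0.066 | 0.078 | 0.055 / 0.055 | 0.056 / 0.062 | 7-8% |

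With the centre effect set to zero and about 10.5 unequal centres, the clustered test still rejected in 11.1% (no covariate) and 12.2% (with covariate). The cause is therefore the small number of clusters and not true centre differences. Blocks of 3 within centre did not cure it: 13-15% with 8 centres, 10-12% with 12, 8-8.5% with 20 and 7-8% with 30.

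The model-based variance gave about 4-6.5% in nearly all settings. Two log-normal settings gave 6.8% and 6.9%; the clustered test gave 9.3% and 10.0% in the same two.

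**Step 4. Familywise error.** Suppose MWT is the only true null. If passing the first four tests is independent of the MWT result, then

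familywise error = (MWT size) × P(first four all significant).

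It exceeds .05 once that probability passes .05/size:
- size 0.08: 0.05/0.08 = 0.625
- size 0.10: 0.05/0.10 = 0.50
- size 0.14: 0.05/0.14 = 0.357

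As an illustration, give all four tests the 0.85 power that SAP 4.2 states for UNS and treat them as independent: 0.85⁴ = 0.522. The familywise error is then 0.042, 0.052 and 0.073 for the three sizes. Correlation between endpoints would change these figures, but the error cannot exceed the MWT size itself. Under the global null it cannot exceed the size of the UNS test.

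**Step 5. Stratified Cox.** Stratifying by centre with model-based variance held its size at 4-6%. With unblocked allocation and unequal centres, where unstratified Cox had 65-71% power, it lost about 10 points at 20 centres and 12-17 at 30. About 11 and 19 of the 108 patients, respectively, sat in centres with only one arm.

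**The case against.** The strongest objection is that the size of the problem depends on a figure the documents do not give. With 30 or 40 centres the inflation is 2 to 4 points. The SAP also leaves the reference distribution open, and a K/(K−1) factor with t(K−1) removes most of the excess. Both points stand. They are why the result is shown by number of centres and tied to an uncorrected Wald test. The correction still leaves 6.2-8.1% when centre sizes differ.

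A reader might infer that MWT would be falsely declared significant in, say, 8-14% of trials. The documents do not support that. MWT is tested only after four other endpoints succeed, so these are rates once MWT is reached. Two of the four, UNS-CTP and WRC, are tested only in type 1 patients, which lowers the chance of getting that far.

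A reader might also infer that the SAP's type 1 claim fails outright. It does not: it holds under the global null, and part of the range in Step 4 lies below .05.

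Two further defences have limited force. SAP 4.1.3.1 does allow other models where specified, so departing from the general model is not itself an error. The fixed-centre analysis already planned for MWT is useful, but it is a sensitivity analysis and does not decide significance. The multiple imputation was not simulated; Rubin's rules do not correct for few clusters.

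**Conclusion.** The concern holds in limited form. For every assumed number of centres from 5 to 40, the MWT test as written, read as an uncorrected Wald test, has a true size above 5% once it is reached: from about 17-22% with 5 centres to 7-8% with 40. The MWT confidence interval is too narrow wherever MWT falls in the sequence.

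Strong control at .05 is not assured at the last step. The bound can be exceeded when UNS, PDSS, UNS-CTP and WRC are effective and usually significant while MWT is null; at a size of 10%, this happens once the chance of reaching MWT is above 0.50. The other four confirmatory tests do not use this variance and are unaffected.

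This should be corrected, but it does not threaten the trial's primary conclusion. The figures rest on the assumed number of centres, 108 analysed patients and the simulated time distributions.

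**What to change.** In SAP 4.5.3.2.4:
- Make the confirmatory MWT test a Cox model with model-based variance. If centre is to be modelled, use a shared random frailty, in line with general Model 1. The size of the frailty version was not simulated and should be checked first.
- Keep the centre-clustered variance as a sensitivity analysis beside the planned fixed-centre analysis.
- Choose centre-stratified Cox only if centres are few or randomisation is blocked by centre, because of the power loss in Step 5.
- If the clustered variance stays confirmatory, prespecify a small-sample correction suited to unequal centres, and its reference distribution.
- State the number of centres.
- Report the hazard ratio with its 95% CI in place of the difference in adjusted means, which a Cox model does not estimate.

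The cost is a short SAP edit and a small programming change, with no new data. The drawback is that model-based variance relies on the Cox model being adequate. Its simulated size was near 5% but not exactly 5%.

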## Missing data handling:

Multiple Imputation (MI) procedure will be used to impute the missing evaluations (Cf.section 4.1.4.1).

## Statistical elements:

For this comparison the following elements will be provided in a summary table:

- Estimate (standard error) of the difference between adjusted treatment group means.
- Two-sided 95% CI of the estimate.
- p-value (to be compared to 0.05).

## 4.5.3.3 Exploratory analysis

#### 4.5.3.3.1 Ullanlinna Narcolepsy Scale EDS subscore (UNS-EDS)

This sub-score EDS is computed for all patients.

#### Analysis:

 The difference between BF2.649 and placebo will be studied in the same way as the primary analysis (with only one sensitivity analysis: the same model as for the primary analysis by actual treatment group, only if actual group is different from randomized group).

In addition,

- Descriptive statistics at baseline and at each post-baseline visit by treatment group and an évolution graph of Mean ± SE will be provided.
- Descriptive statistics at baseline and at each post-baseline visit by treatment group of the response to the treatment will be provided.

#### Missing data handling:

Missing evaluations are not imputated.

## Statistical elements:

For this comparison the following elements will be provided in a summary table:

- Estimate (standard error) of the difference between adjusted treatment group means.

- Two-sided 95% CI of the estimate.
- p-value (to be compared to 0.05).

## 4.5.3.3.2 Clinical Global Impression of improvement

Clinical Global Impression of improvement is measured for EDS and cataplexy at V6, V7 and V8.

#### **Definition:**

This endpoint is defined as the value at the end of each period (V2-V7 and V7-V8) in Global Improvement (CGI-I).

#### Analyses:

The difference between placebo and BF2.649 will be studied at end of each period using a two-sided Student's t-test for independent samples and a Mann-Whitney test.

## Missing data handling:

Missing evaluations are not imputated.

## Statistical elements:

For these comparisons the following elements will be provided in a summary table:

- Estimate (standard error) of the difference between treatment group means
- Two-sided 95% CI of the estimate.
- P-value from two-sided Student's t-test for independent (to be compared to 0.05).
- P-value from Mann-Whitney test (to be compared to 0.05).

## 4.5.3.3.3 Response to treatment according to the CGI-C

An alternative calculation of CGI-C consists in evaluating the number of patients experiencing at least an improvement (CGI-CI) and defined as responder to therapy.

#### Definition:

This endpoint is defined as the value at end of each period in the response to treatment (based on CGI-I).

## Missing data handling:

Missing evaluations are not imputated.

## Analyses:

The difference between placebo and BF2.649 will be studied at end of each period using a Chi-Square test.

In addition, descriptive statistics at baseline and at each post-baseline visit by treatment group.

## Statistical elements:

For these comparisons the following elements will be provided in a summary table:

- Estimate (Standard Error) of the difference between the proportions of patients.
- Two-sided 95% CI of the estimate.
- P-value from Chi-2 test (to be compared to 0.05).

## 4.5.3.3.4 Child and Adolescent Sleepiness Scale (CASS)

ESS version adapted for children (6 and over) and adolescents (CASS) with range [0, 30], A score greater than 14 is considered as abnormal sleepiness. CASS will be evaluated at each study visit of double-blind phase and reviewed by the investigator.

#### Analysis:

The difference between placebo and BF2.649 will be studied in the same way as the primary analysis (Excluding sensitivity analysis).

In addition,

 Descriptive statistics at baseline and at each post-baseline visit by treatment group will be provided

Missing data handling:

Missing evaluations are not imputated

#### Statistical elements:

For this comparison the following elements will be provided in a summary table:

- Estimate (standard error) of the difference between adjusted treatment group means.
- Two-sided 95% CI of the estimate.
- p-value (to be compared to 0.05).

#### 4.5.3.3.5 Test of Everyday Attention for Children (TEA-Ch)

The Test of Everyday Attention for Children (TEA-Ch) assesses the cognitive functions with a version A at V1 and a version B at V6.

A reference table « TeaCH\_tests» can do the correspondance between the code in databe and the item.

Analysis:

Cumulative percentages will be used in analyses (It's more meaningfull than raw scores to compare children according their sex and age)

The difference between placebo and BF2.649 will be studied, by test, in the same way as the primary analysis (Excluding sensitivity analysis).

In addition,

 Value and change from baseline descriptive statistics by visit, by treatment group will be provided.

Missing data handling:

Missing evaluations are not imputated

#### 4.5.3.3.6 Patient sleep diary

The Weekly rate of cataplexy (partial and total) analysis is already done in the secondary endpoint (section 4.5.3.2.3).

The other calculated parameters are:

- Night duration calculated as the difference between Hour of bedtime and wake-time (NightD)
- Number of diurnal involuntary sleep attacks and episodes of severe daytime sleepiness (NSAE).

- Number of hallucinations and sleep paralysis episodes (NHS).

#### Analysis:

Descriptive statistics by treatment group during the following intervals: Baseline (D-28 to D0), Final DB last 6 weeks DB4=D21-D63, Final DB last 2 weeks: DB2=D49-D63 will be provided

Missing data handling:

Missing evaluations are not imputated

#### 4.5.3.3.7 Patient's Global Opinion on the effect of treatment

At V7 patients' global opinion will be reported by patient if able to express himself. If not, either their parents or their main teachers should evaluate the Global effect of the treatment by comparing the period prior to that visit with the patient's pre-study condition. The six-level of the PGO will be 3= Marked effect, 2=Moderate, 1=Minimal, 0=No, -1= Minimal Worse, -2=Much worse.

We also use the binary variable PGO-C defined as patient having Improved (when PGO=3, 2 or 1) and considered as responder to therapy

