3.7.1.2.7. Patient's Global Opinion on the effect of treatment

At V7 and all visits of open-label period, patients' global opinion will be reported by patient if able to express himself. If not, either their parents or their main teachers should evaluate the Global effect of the treatment by comparing the period prior to that visit with the patient's prestudy condition.

The following six-level scale will be used:

- Marked effect (complete or nearly complete remission of EDS)
- Moderate effect (partial remission of EDS)
- Minimal effect (slight decrease in EDS that does not substantially alter the status of the patient)
- No change
- Minimally worse (slight increase in EDS)
- Much worse (substantial increase in EDS)

3.7.1.3. Compliance

The compliance with study medication will be assessed by comparing the amount of medication remaining at each visit with the amount predicted to remain if the patient is compliant with the prescription.

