# **Definition:**

This endpoint is defined as the value at V7 in the response to treatment (based on PGO-C).

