## Analyses:

The difference between placebo and BF2.649 will be studied at V7 using a Chi-2 test. In addition, descriptive statistics of levels by treatment group will be provided

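### The Patient's Global Opinion is tested between arms only as any improvement versus none; the six ordered levels are described but not tested, unlike CGI

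*SAP*

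**What the plan says.** Protocol section 3.7.1.2.7 defines six levels of patient opinion. Marked effect is complete or nearly complete remission of EDS, and moderate effect is partial remission. Minimal effect is a "slight decrease in EDS that does not substantially alter the status of the patient". The other levels are no change and two grades of worsening. The protocol defines no responder on this scale.

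SAP section 4.5.3.3.7 codes the levels as "3= Marked effect, 2=Moderate, 1=Minimal, 0=No, -1= Minimal Worse, -2=Much worse". It then introduces PGO-C, "defined as patient having Improved (when PGO=3, 2 or 1) and considered as responder to therapy". The endpoint is PGO-C at V7, and the inference is one sentence: "The difference between placebo and BF2.649 will be studied at V7 using a Chi-2 test". The next sentence adds: "In addition, descriptive statistics of levels by treatment group will be provided". The chi-square p-value is the only one listed for the summary table.

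The endpoint sits under the SAP's exploratory analyses (4.5.3.3). Section 4.1.3.2 limits the fixed testing sequence to UNS, PDSS, UNS-CTP, WRC and MWT and calls all other endpoints exploratory and supportive. Protocol section 3.3.2 does list patient opinion among the secondary endpoints.

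For CGI, SAP section 4.5.3.3.2 tests the improvement score by Student's t-test and Mann-Whitney, and section 4.5.3.3.3 also tests a responder dichotomy by chi-square.

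**The concern.** Two features combine. First, the responder label includes children whose change, in the protocol's own words, leaves their status not substantially altered. A reader of the report will probably take a responder to be a child with worthwhile benefit. Second, this dichotomy carries the whole between-group inference. It treats a marked effect like a minimal one, and no change like much worse. An improvement among children already above the cut cannot affect the p-value.

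The SAP gives no reason for handling PGO differently from CGI, a comparable ordered scale. What is at stake is the sensitivity and interpretation of one supportive result.

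**Working it through.** **Plan's own figure.** There is none: neither document gives a PGO response rate, power or sample size. The textual point follows from the passages above. The arithmetic below illustrates size only.

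**Inputs from the documents.** 36 placebo and 72 pitolisant children (SAP 4.2, sized on UNS); two-sided 0.05 (SAP 4.1.6); six levels with the responder cut at PGO ≥ 1 (SAP 4.5.3.3.7). Every child is taken to have a V7 rating. The SAP does not impute PGO, so fewer would contribute if any are missing.

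**Assumptions.** Three placebo distributions, in % from much worse to marked:
- Low: 5/10/50/20/10/5 (35% at PGO ≥ 1)
- Middle: 5/10/35/25/17/8 (50%)
- High: 3/7/25/30/22/13 (65%)

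The treatment effect is a common odds ratio (OR) at every cut: odds(PGO ≥ k, pitolisant) = OR × odds(PGO ≥ k, placebo).

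**Worked case: middle distribution, OR 2.**
- PGO ≥ 1: placebo 0.50, odds 1; pitolisant odds 2, so 0.667.
- Pooled proportion = (36×0.50 + 72×0.667)/108 = 0.611.
- Null SE = √[0.611×0.389×(1/36 + 1/72)] = 0.0995.
- Alternative SE = √[0.50×0.50/36 + 0.667×0.333/72] = 0.1001.
- Power = Φ[(0.1667 − 1.96×0.0995)/0.1001] = Φ(−0.28) ≈ 0.39.

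Simulation (20,000 trials) gives 0.390 for this chi-square. The rank test used the tie-corrected Wilcoxon variance, n₀n₁/12 × [(N+1) − Σ(t³−t)/(N(N−1))], where t is the number of children at each level. It gives 0.468.

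**All cases (simulated power).**

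| Placebo PGO ≥ 1 | OR | Chi-square, PGO ≥ 1 (planned) | Rank test, six levels | Gain, points | Chi-square, PGO ≥ 2 |
|---|---|---|---|---|---|
| 35% | 2 | 0.373 | 0.440 | 7 | 0.246 |
| 35% | 2.5 | 0.597 | 0.676 | 8 | 0.430 |
| 35% | 3 | 0.755 | 0.827 | 7 | 0.596 |
| 50% | 2 | 0.390 | 0.468 | 8 | 0.340 |
| 50% | 2.5 | 0.597 | 0.701 | 10 | 0.551 |
| 50% | 3 | 0.739 | 0.847 | 11 | 0.718 |
| 65% | 2 | 0.354 | 0.476 | 12 | 0.380 |
| 65% | 2.5 | 0.526 | 0.700 | 17 | 0.594 |
| 65% | 3 | 0.656 | 0.848 | 19 | 0.753 |

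With OR 1, the planned chi-square rejects in 4.8% to 5.1% of trials and the rank test in 4.6% to 4.9%. Both hold their level.

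**Two deliberately extreme patterns (middle distribution).**

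| Only change under pitolisant | PGO ≥ 1 rate | Chi-square, PGO ≥ 1 | Rank test | Chi-square, PGO ≥ 2 |
|---|---|---|---|---|
| 15% of patients move from minimal to marked | 50% in both arms | 0.05 | 0.13 | 0.34 |
| 25% of patients move from no change to minimal | 50% → 75% | 0.74 | 0.28 | 0.05 |

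The planned test cannot see the first pattern. In the second it is driven entirely by a change that the protocol calls not substantial, and there it is much stronger than the rank test.

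**The case against.** The case for leaving the plan alone is substantial, and most of it stands.

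- **No decision rests on this endpoint.** It is outside the fixed sequence, so low power here changes no confirmatory conclusion.
- **A reader might infer that the six-level scale is wasted.** It is not. The levels are reported by arm, and the proportion with moderate or marked effect can be read from that table. Only the inference ignores the grades.
- **A reader might infer that the cut contradicts the protocol.** The protocol defines no PGO responder, and a slight decrease in EDS is literally an improvement. The cut also follows the SAP's own convention: SAP 4.1.5.5 counts minimally improved as a CGI response. The difference is that protocol section 3.7.1.2.3 attaches no comparable qualification to that CGI grade, and CGI keeps a full-scale test.
- **A reader might infer that the responder comparison is biased because minimal effects raise the rate.** The cut is prespecified and applied identically to both blinded arms, and type I error is unaffected. The rate needs an accurate label; the comparison is not distorted.
- **The power ranking depends on assumption.** A common odds ratio favours the rank test, and the no-change-to-minimal pattern reverses the ranking.

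None of this explains why PGO lacks the full-scale test that CGI receives.

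**Conclusion.** The point holds as a minor improvement. The sole PGO inference is a chi-square on any improvement, its responder label includes change that the protocol words as not substantial, and the six levels go untested although the SAP tests the corresponding CGI score.

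The textual part needs no assumption. The gain of about 7 to 19 points of power rests on the three assumed placebo distributions, a common odds ratio of 2 to 3, and complete V7 data on 36 and 72 children.

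The documents do not support a demand to move the responder cut to moderate or marked effect. That cut would sit closer to the protocol's wording but gives no consistent power gain: it is weaker than the planned cut in the 35% and 50% scenarios and stronger in the 65% scenario. Moving it for PGO alone would also leave two responder conventions in one report. It remains optional.

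**What to change.** In SAP section 4.5.3.3.7:

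1. Add a between-group test on the six-level PGO at V7, either Mann-Whitney (as for CGI) or a proportional-odds model. Name it in advance as the main PGO comparison.
2. Keep the PGO ≥ 1 chi-square as supportive, and relabel that proportion *any improvement*.
3. Keep the planned table of levels by arm, from which the moderate-or-marked proportion can be read.

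The data are already collected, so visits and CRF do not change. The cost is one more exploratory p-value, and a main PGO test that is less sensitive if the drug only moves children from no change to minimal effect. The retained chi-square covers that case.
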